4.4 Target Areas

The Target Area will be defined for TPE localities as all individuals residing within 200m of an index case that is detected in passive surveillance and resides in a TPE study locality, with individuals residing immediately beyond 200m included if a minimum of 30 individuals are not enrolled within 200m. This Target Area size was selected based on the existing RACD data whereby the mean number of individuals screened per index case was 32.

The Target Area will be defined for RACD localities as all individuals residing within 500m of an index case that is detected in passive surveillance and resides in a RACD locality. The malaria surveillance team will be trained to focus on maximizing coverage within the immediate 200m radius around the index case. This Target Area size was selected based on the current RACD policy in Swaziland.

Based on collected data on missing individuals, the estimated total number of individuals residing within 200m of an index case is 53. Thus, coverage to date for RACD has been 60%. However return visits do not typically occur at off hours (mornings and evenings). Moving forward, at least one return visit must occur during off-hours to ensure better capture and to maximize the sample size.

If a subsequent index case is reported in a target area (identified either through health facilities or RACD (all secondary cases identified in RACD become index cases)), the RACD intervention will not be repeated within 5 weeks (per current national policy). For the TPE arm, the intervention will not be repeated within 8 weeks or more than twice within the past year (DP drug insert recommends no repeat course within 8 weeks, and no more than 2 courses within one year).

Target Areas that reside on the border between two localities that were randomized to different arms will receive the intervention according to the locality randomization of the index case. For outcome measures, some contamination of the intervention arm's effect may occur if a neighboring locality is randomized to a different intervention. In the analysis we will adjust for distance from an index case for whom the surrounding area received TPE intervention. It will not be necessary to adjust for distance from an area where RACD was conducted because RACD is the current standard of care in all receptive areas of the country.

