4.5 Inclusion and exclusion criteria

Table 3. Inclusion and exclusion criteria

	Inclusion criteria	Exclusion criteria
Index case (as trigger for RACD or TPE in their household members and neighbors)	
 • Malaria infection (either locally transmitted or imported) detected at a health facility through passive surveillance, and • Resided in a study locality. 	
 • Malaria infection identified through screening.
RACD intervention	
 • Non-index case, and • Resided or spent at least one night in the Target Area in the past 5 weeks. 	
 • Target Area overlaps with prior Target Area that received the RACD intervention within the past 5 weeks.

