7.2 RACD arm - Perform RDT and refer secondary cases to health facilities

Individuals residing in RACD clusters will be tested by RDT using the *Pf*-specific First Response RDT during the intervention visit. At the time that blood is collected for RDT testing, the same finger prick will be used to generate a slide and dried blood spot. Four spots of blood will be collected for each DBS. Subjects testing positive by RDT will be referred to the closest health facility for treatment according to national policy (first line AL, second line Oral quinine for uncomplicated malaria).

Secondary cases detected by RDT will become index cases (using the same unique study ID) and receive a case investigation. For these secondary cases, a second finger prick will also be performed to collect 250uL blood in a microtainer. These secondary cases will also be invited to participate in the 6-9 months follow-up as well as the end-line survey at the end of the study (expected mid 2017).

The microtainer samples collected from secondary cases will be used to develop serologic and genotyping methods. The rationale for a larger volume of blood is that serum is the gold standard sample for serologic assessment. Although DBS collection is more practical and has been validated for use in population level serologic assessments (as will be done at the end-line survey at the end of the study, expected mid 2017) [19], this microtainer sample will be used to develop and validate our serologic assay. A larger volume of blood draw will also facilitate genotyping. Secondary cases are mainly asymptomatic individuals with low-density infections. In our experience, microsatellites do not usually amplify well when using DBS in asymptomatics.

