14.2 Outcome measures

Table 6. Outcome measures

Outcome	Indicator
Primary Aim	
Incidence	Cumulative incidence of all cases (Pf infection) identified by passive surveillance in the locality subsequent to the first reported case during the study period (not including additional cases found through RACD). Cases include both locally acquired and imported infections.
Secondary aims (effectiveness)	
Exposure (seroprevalence)	Seroprevalence to markers of recent exposure using ELISA in end-line survey samples taken from residents in Target Areas near the end of the study (expected mid 2017), excluding index cases detected through passive surveillance.
Infection prevalence	Prevalence of infection by LAMP and QTNASBA testing for gametocytes in LAMP positives in end-line survey samples taken from residents in Target Areas near the end of the study (expected mid 2017), including index cases detected through passive surveillance.
Time to first local post-intervention incident case	Time to first incident local case in the Target Area subsequent to the intervention. Target Areas that receive a repeat intervention will qualify to be included again at subsequent interventions.
Proportion of imported incident cases	Proportion of imported incident cases in the locality subsequent to the first reported case will be measured through passive surveillance. Additional cases found through RACD will not be included.
Transmission potential (by genotyping)	Microsatellite genotyping will be performed on samples collected from index cases as well as secondary cases.
Secondary aims (feasibility)	
Coverage	Proportion of persons residing within approximately 200m (TPE localities) or 500m (RACD localities) of the index case who consented to participate in the study and who completed the initial procedures for their study arm (finger prick for RDT in the RACD arm, initial dose of DP in the TPE arm)
Adherence	Proportion of persons who completed 3 days of therapy among all individuals initiated on DP in the TPE arm, as assessed by pill count
Prevalence of SAEs related to treatment	Proportion of subjects experiencing SAEs deemed possibly, probably, or definitely related to DP or AL, out of the total number of subjects enrolled
Acceptability	Qualitative assessment (See Section 10)
Cost	Cost per index case-level intervention, cost per case averted.

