4. Comparison of time to first post-intervention incident infection. We hypothesize that time to the first post-intervention index case within the Target Area will be longer for Target Areas receiving TPE compared to those receiving RACD. Analysis for this outcome will use a standard cox proportional hazards model to estimate the time to a subsequent incident infection among individuals in the Target Area.
5. Comparison of transmission potential using genotyping. Microsatellite genotyping will be used to measure transmission potential. DNA samples for genotyping will be collected from index cases and secondary cases. Based on malaria rates in Swaziland over the past three years, we expect approximately 200 index cases over the study period and 35 infections from the follow-up cross sectional survey (1.6% prevalence in the TPE arm and 0.4% in the RACD arm). We expect transmission potential to be lower in the TPE versus RACD arm. Relatedness of infections within Target Areas and within localities will be used as a surrogate for transmission potential.

Planned Analyses of Operational Feasibility and expected findings:

1. Coverage of the intervention. The numbers and proportion of the population completing finger prick testing (if RACD arm) or receiving at least the first dose of medication (if TPE) will be calculated by arm. The proportion of the individuals living in Target Areas around an index case that receive the TPE intervention is expected to be 80% with a 95% confidence interval from 76% to 84%.
2. Adherence to TPE. In the subsample of Target Areas surrounding the first index case in each locality assigned to TPE, we will assess adherence to the 3 day regimen of DP in TPE using pill count. We expect adherence to be 80%.
3. Safety of the TPE treatment. The number and percent of individuals experiencing an adverse event will be recorded by study arm. We expect that compared to RACD, TPE will be safely administered with few or no serious adverse events related to treatment, and no difference in SAEs compared to AL based on analysis of the adverse events report forms.
4. Acceptability of the intervention. See Section 10.
5. Costs per incident infection and per population. Detailed costing will be performed in 10 Target Areas per arm. We expect that costs per incident infection and per population for implementing the TPE intervention will be no higher than for RACD, the current standard of care.

15 Advisory Committee

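### The documents conflict on whether infections found by RACD testing count as events for time to first post-intervention local case; if they count, the hazard ratio would favour TPE under no effect

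*Combined protocol and SAP*

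**What the plan says.** Table 6 in 14.2 gives the event for this outcome as "Time to first incident local case in the Target Area subsequent to the intervention". That row does not say how the case must be detected. Two neighbouring rows do: the primary incidence row adds "not including additional cases found through RACD", and the imported-proportion row adds "Additional cases found through RACD will not be included".

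Section 14.4, secondary analysis item 4, states the hypothesis as "time to the first post-intervention index case within the Target Area will be longer for Target Areas receiving TPE compared to those receiving RACD". The next sentence describes the Cox model as estimating time to a subsequent incident *infection* among people in the Target Area.

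Three passages bear on what an index case is:

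- Section 4.4 allows a subsequent index case in a Target Area to come from a health facility or from RACD, because "all secondary cases identified in RACD become index cases".
- Section 7.2 repeats this: "Secondary cases detected by RDT will become index cases (using the same unique study ID) and receive a case investigation".
- Table 3 in 4.5 says the opposite. It lists "Malaria infection identified through screening" as an exclusion for index cases.

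On data source, 9.4 lists this outcome among the passively collected incidence measures, and the timeline in section 18 places it under routine surveillance.

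**The concern.** Someone programming the Cox model would work from the Table 6 row and 14.4 item 4. Neither contains a passive restriction. An analyst who then looks up *index case* in 4.4 or 7.2 would count RACD finds as events. One who looks it up in Table 3 would not. Both could claim to follow the protocol.

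The choice matters because testing differs by arm. In RACD areas everyone within 500 m is to be offered an RDT, over up to three visits (6.2, 7.2). In TPE areas only residents who cannot safely take DP are tested (7.3). If test-found infections count, ascertainment is active in one arm and largely passive in the other. RACD areas would then tend to reach the event sooner because people were tested, not because transmission was higher. That is the direction the trial hypothesises in section 3. A choice of this kind should not be left open until data have been seen.

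**Working it through.** **Plan's own figure.** There is none to reproduce. Table 9 gives n/a as the expected result for this outcome. It lists only a population, whose effective size checks as 63 × 656 = 41,328.

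**What each passage implies about RACD finds**

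| Place | Implication |
|---|---|
| 14.2, Table 6, this row | Silent |
| 14.2, Table 6, incidence and imported-proportion rows | Excluded, for those outcomes |
| 14.4 item 4 | Event is an index case, then an incident infection |
| 4.4 and 7.2 | RACD finds become index cases |
| 4.5, Table 3 | Screening finds are not index cases |
| 9.4 and section 18 | Passive or routine surveillance data |

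**Illustration under no effect.** Let p be the chance that a Target Area has a later passively detected local case, the same in both arms. Let q be the chance that an RACD Target Area gains an event from testing. The limited testing in the TPE arm is set to zero.

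- RACD event risk = 1 − (1 − p)(1 − q)
- Apparent hazard ratio, TPE to RACD, taken as the ratio of cumulative hazards = ln(1 − p) / [ln(1 − p) + ln(1 − q)]

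**Inputs**

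- Share of RACD events that find at least one further infection by RDT: 11.4% (section 1.3).
- Local share: 236/333 = 0.709 (Table 2 totals for incident cases). Applying it to RACD finds is an assumption.
- Share of encounters in people who already received an intervention, through repeated or overlapping Target Areas: 10% (14.1). Using it as a proxy for repeat-round testing is an assumption.
- p is not in the documents. A range of 10% to 40% is assumed.

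**Three readings**

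1. Passive only: q = 0, so the null hazard ratio is 1.00.
2. Only finds at repeat rounds count: q = 0.10 × 0.114 × 0.709 = 0.0081.
3. All first-round finds count: q = 0.114 × 0.709 = 0.0808.

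Worked example for reading 3 at p = 10%: ln(0.9) = −0.1054 and ln(0.9192) = −0.0842, so the ratio is 0.1054 / (0.1054 + 0.0842) = 0.56.

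| p | RACD risk, reading 2 | Null HR, reading 2 | RACD risk, reading 3 | Null HR, reading 3 |
|---|---|---|---|---|
| 10% | 10.7% | 0.93 | 17.3% | 0.56 |
| 20% | 20.6% | 0.96 | 26.5% | 0.73 |
| 30% | 30.6% | 0.98 | 35.7% | 0.81 |
| 40% | 40.5% | 0.98 | 44.8% | 0.86 |

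If every RACD find were local (q = 0.114), reading 3 would give 0.47, 0.65, 0.75 and 0.81.

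**The case against.** The best defence is that the protocol as a whole intends passive cases. Besides Table 3, 9.4 and the timeline, the rationale in section 2 describes incidence as coming from health facility reports and missing asymptomatic infections. Sections 4.1 and 9.1 also describe incidence data as passive. Table 2 keeps incident and secondary cases in separate columns, and its footnote ties secondary cases to reactive case detection. The phrase in 4.4 sits in a rule about repeating the intervention, and 7.2 concerns case investigation. Neither defines this outcome. Much of this stands, and it is why the point is a conflict and not an established bias.

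It does not settle the matter. Section 9.4 is not a reliable definition: it describes incidence as local cases, whereas Table 6 counts local and imported, and it calls this event an end-line case. Table 3 is contradicted outright by 4.4 and 7.2.

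A second objection is that most RACD finds arise during the intervention visits, so they are not subsequent to the intervention. That is fair, and it is why reading 3 is an extreme. But no time origin is stated, so the text does not rule it out.

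A third is that a repeat round follows a case that is already the first event. This is true when the trigger is a passively detected local case inside the Target Area. It fails when the trigger is imported (97 of 333 cases in Table 2, and imported cases also trigger the intervention under 4.2) or lies in an overlapping neighbouring area.

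A reader might infer the stronger claim that RACD does gain events and that the hazard ratio is therefore biased to 0.56–0.86. The documents do not support it. It needs RACD finds to count and all first-round finds to fall after an unstated time origin.

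**Conclusion.** The event definition is internally inconsistent and should be resolved before analysis. Any bias is conditional: it exists only if RACD finds are counted, and then its direction favours TPE. For p of 10% to 40%, the null hazard ratio is 1.00 on the passive reading, about 0.93 to 0.98 if only repeat-round finds count, and 0.56 to 0.86 at the upper extreme. The effect thus runs from nothing to large.

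These figures rest on the assumed p, the 71% local share, the 10% proxy for repeat testing, and no modelled benefit from treating RACD finds. The value of 1.00 concerns this mechanism alone. The different Target Area radii (200 m and 500 m) are a separate matter.

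The outcome is secondary and has no power calculation, but it is one of the listed effectiveness comparisons. The correction is worth making because it removes a contradictory rule at almost no cost.

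**What to change.** - **Table 6, time-to-first row:** add *identified by passive surveillance; cases found through RACD or any other study testing in either arm will not be included*. This extends the exclusion already used in the imported-proportion row, and it covers the RDTs done in the TPE arm.
- **14.4 item 4:** replace *index case* and *incident infection* with *passively detected local case*.
- **Time origin:** state it, for example as completion of the intervention in the Target Area.
- **Data handling:** for this outcome, use Appendix C item 51, which already codes secondary cases from RACD separately, to remove them.
- **4.4 and 7.2 against Table 3:** reconcile the index-case wording, without changing when interventions are repeated or which index cases enter the seroprevalence analysis. Redefining *index case* for every outcome would go too far: 14.3 includes later index cases in the seroprevalence sample, and 4.4 uses the term in its repeat rule.

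The cost is a few wording changes and no new data. The loss of RACD events depends on the reading replaced. At p = 10% it is none on the passive reading, about 7% on the repeat-round reading ((10.7 − 10)/10.7), and about 42% at the extreme ((17.3 − 10)/17.3). The events lost are those that arise only from testing.

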9.3 End-line survey (at the end of the study, expected mid 2017)

Towards the end of the study, all residents of Target Areas will be requested to participate in blood collection by DBS. Subjects who did not participate in the intervention are eligible for participation as the goal of the study is to evaluate the impact of the intervention on the community level. In addition to blood collection, we will ask a few short questions about malaria exposure since the intervention. The same barcode will be used to label the blood sample, linking the sample to the same participant. The date of collection will also be used to label the blood sample to differentiate this blood sample from previously collected blood samples (Appendices H & I). Study staff will return for up to 1 additional visit to ensure high capture.

The main purpose of the end-line survey is to perform serology. A serological assessment looking at markers of recent exposure will enable comparisons of recent transmission (and thus impact of RACD vs. TPE) between the two arms. A serological assessment looking at markers of past exposure will enable comparisons of baseline exposure between the two arms. We will also use this measure to look at antibody kinetics (in relation to the baseline and 6-9 month capture points). These samples will also be used to measure infection prevalence.

While the total sample size for the study is expected to be 6000 based on RACD data, we anticipate that 10% of these encounters will occur in individuals that will have received the intervention twice (repeat Target Area enrolled more than 5 weeks since the prior RACD intervention, or more than 8 weeks since the last TPE intervention). These individuals only need to be sampled once. Therefore, we expect to screen about 5400 individuals. While some may not be present to participate in the end-line survey, we expect to also recruit new individuals who were not previously present at the time of the intervention. This sample size will enable us to detect a difference of 3% seroprevalence in the TPE versus 0.6% in the RACD arm (Table 8).

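### Time to first local case: records re-enter under repeat rules that differ by arm, giving a small, conditional bias towards TPE that a first-entry analysis removes

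*Combined protocol and SAP*

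**What the plan says.** Section 14.2, Table 6 defines the outcome as the time to the first local incident case in a Target Area after the intervention, and adds: "Target Areas that receive a repeat intervention will qualify to be included again at subsequent interventions".

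Section 4.4 sets when an intervention may be repeated. In the control arm, "the RACD intervention will not be repeated within 5 weeks (per current national policy"); no yearly limit is stated. The other arm has a longer gap and a cap: "For the TPE arm, the intervention will not be repeated within 8 weeks or more than twice within the past year". Section 9.3 restates the two gaps when it describes repeat enrolment: "repeat Target Area enrolled more than 5 weeks since the prior RACD intervention, or more than 8 weeks since the last TPE intervention".

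Section 14.4 gives the model: "Analysis for this outcome will use a standard cox proportional hazards model". It says that Target Area analyses will account for clustering by locality and by index case area. It has no provision for a Target Area's second and later records.

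On the event, Section 14.4 hypothesises that "time to the first post-intervention index case within the Target Area will be longer for Target Areas receiving TPE", and Section 4.4 says that "all secondary cases identified in RACD become index cases" (Section 7.2 agrees). Table 3 in Section 4.5, however, excludes infections found by screening from being index cases. The incidence and imported-proportion rows of Table 6 leave out cases found through RACD; the time-to-first-case row is silent.

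**The concern.** A new record starts only when the intervention is repeated, and the rule for repeating is part of the arm. Suppose that an area in either arm has its first intervention at week 0 and local index cases at weeks 6, 14 and 24.

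- **RACD:** each case is at least 5 weeks after the last intervention, so records start at weeks 0, 6, 14 and 24. The completed intervals are 6, 8 and 10 weeks.
- **TPE:** the week-6 case falls inside the 8-week gap and starts nothing. The week-14 case starts a second record. The week-24 case would be a third intervention within a year and starts nothing. The completed intervals are 6 and 10 weeks.

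The case history is identical, but this active area contributes four records to one arm and two to the other. A quiet area contributes one in either arm. The RACD records are therefore weighted more heavily towards high-risk areas, and the RACD hazard looks higher. A robust or clustered variance changes the standard error and leaves this mix as it is, so the point estimate stays shifted. The shift is in the direction of the trial's hypothesis, on a named effectiveness aim.

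**Working it through.** **The plan's own figure.** The only stated figure that uses repeats is the end-line sample in Section 14.1: 200 index cases x 30 people = 6000 encounters, and 6000 x (1 - 0.10) = 5400 individuals. This reproduces exactly. The 10% is not split by arm and refers to encounters; it is used here as the share of records that are repeats. Table 9 gives no power calculation for this outcome, and no event count or HR is stated.

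**Inputs to a simulation with no effect**

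- Repeat rules from Section 4.4. RACD: at least 5 weeks since the last intervention. TPE: at least 8 weeks, and fewer than two interventions in the past 52 weeks.
- Share of cases that are local, from Table 2: 236/333 = 71%. Local and imported cases both trigger an intervention; only local cases are events.
- Follow-up of 92 weeks, an assumption for September 2015 to mid-2017.
- Spread of risk between Target Areas: not given. It is varied as a gamma distribution with shape 1, 0.5 or 0.2, plus equal risk. The only coefficient of variation in the plan is 0.9 (Section 14.3, between localities), which corresponds to shape 1/0.9² = 1.23.

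The same simulated cases were passed through both repeat rules. An area enters at its first case, as in the protocol. Each intervention is a record in a Cox model on time since intervention.

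**Null HR, all records, by RACD repeat share**

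| Risk between areas | 10% | 20% | 30% |
|---|---|---|---|
| Equal | 1.00 | 1.00 | 1.00 |
| Gamma, shape 1 | 1.00 | 0.98 | 0.97 |
| Gamma, shape 0.5 | 0.99 | 0.98 | 0.96 |
| Gamma, shape 0.2 | 0.99 to 1.00 | 0.97 | 0.95 |
| Shape 0.5 with outbreak clustering | 0.98 | 0.98 | 0.97 |
| Shape 0.2 with outbreak clustering | 0.98 to 0.99 | 0.98 to 0.99 | 0.96 |

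Outbreak clustering here means that each case seeds on average 0.1 further local cases. At 10% RACD repeats, the TPE share was about 9%, or 5-6% with outbreak clustering. At about 50% RACD repeats (TPE 40-41%), the HR was 0.89 to 0.93. A second null simulation put the shift relative to first-entry-only at about 1-3% at 10% repeats and about 3-11% at 30-55%.

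**Error rate.** At 10% repeats and about 100 interventions per arm, false rejection in favour of TPE with robust standard errors was 1.5-2.8%, against a nominal 2.5% (two-sided 0.05 assumed). There is no visible inflation.

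**Extreme case.** Treating each of the 63 localities with cases in Table 2 as a single Target Area, at its own rate, gives repeat shares of 69% and 55% and a mean null HR of 0.84. Two-sided type I error is 11.4% with robust standard errors, of which 10.1 points favour TPE. This is an upper bound: a locality is far larger than a Target Area.

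**After the change.** With the first record only, the mean null HR in that extreme case is 0.998. With one common re-entry rule in both arms, large-sample null HRs were 0.97 to 1.02, consistent with 1 within simulation error.

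**The case against.** The strongest reply is that the effect is negligible at the plan's own figures. At 10% repeats the shift is about 3% at most, the error rate does not move, and the outcome is secondary, unpowered and built on about 200 index cases. A shift of that size lies well inside sampling error. This stands, and it limits the point to a cheap improvement.

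It can also be said that the response event is a legitimate unit, so re-entry is a reasonable choice. That stands for re-entry as such, but not for re-entry governed by a different rule in each arm. The overlap exclusions in Table 3 act on 500 m and 200 m areas and may offset some of the imbalance; this was not modelled.

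Two stronger readings are tempting.

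- **A large bias.** Simulations in which entry is unrelated to an area's own case rate, with gamma shapes of 0.1-0.5, give null HRs of 0.79 to 0.97. Those shapes imply coefficients of variation of about 1.4 to 3.2, against the one documented value of 0.9. A Target Area also exists only because an index case arose there, so where that case is local, entry already selects higher-rate areas. With entry by a local case, or with a coefficient of variation of 0.9, the HR was 0.97 to 0.99.
- **RACD-detected infections counted as events.** A reader might infer this from Sections 4.4, 7.2 and 14.4, and apply the 11.4% of past RACD events that found an RDT-positive person (Section 1.3). Section 9.4 lists this outcome among passively collected measures, the Section 18 timeline takes it from routine surveillance, and Table 3 bars screened infections as index cases. The documents largely rule that reading out. What remains is a wording conflict.

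**Conclusion.** The point holds as a conditional bias in favour of TPE. It needs risk to differ between Target Areas. Section 1.2 says that transmission is heterogeneous, and in Table 2 eight of the 77 localities hold 165 of 333 cases (50%), one of them 41. How far that carries down to Target Areas is not documented, so every size other than zero under equal risk depends on an assumed spread.

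On the plan's expected repeat share the bias is too small to change a conclusion. It becomes material only with repeats well above plan or with cases confined to a few hot spots. Neither can be excluded: the 10% comes from preliminary RACD data, and Section 4.4 notes that, for a time, capacity limits kept some eligible index cases from receiving RACD. The arm-dependent selection of records is avoidable, which is sufficient reason to remove it before the data are seen.

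**What to change.** In Table 6 and the matching item of Section 14.4:

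1. Make the lead analysis one record per Target Area, starting at the first intervention there during the study, and remove the re-entry sentence from the outcome definition.
2. Keep all records as a sensitivity analysis. Start new records from index-case dates by a single spacing rule, fixed in advance and identical in both arms, whether or not the intervention was actually repeated.
3. As a clarification only, state in this row that cases found through RACD are not included, in line with Section 9.4. Reconcile Sections 4.4 and 7.2, where RACD-detected cases become index cases, with Table 3, where screened infections are excluded as index cases.

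The cost is wording, plus about 10% of intervals in the lead analysis at the expected repeat share, a small loss of precision. Field procedures and the repeat-intervention schedules stay as they are. The change does not address the separate difference in radius (500 m versus 200 m) between the arms' Target Areas.
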